Upstaged to pN2	YES: if pathological disease stage of primary tumour = N2 NO: if pathological disease stage of primary tumour = N0 OR N1 NOT CANCER: no cancer, sample benign MISSING: otherwise

6. Overall and disease-free survival to 1 year

Both overall and disease-free survival to 12 months will be compared between groups.

New variable	Rules
Time to death (days)	(Death date – randomisation date)
Death censor variable	YES: if patient did not die before the end of follow-up NO: if patient died before the end of follow-up MISSING: otherwise
Time to disease progression (days)	(Date of earliest disease recurrence – randomisation date)
Disease progression censor variable	YES: if patient did not have disease progression before the end of follow-up NO: if patient had disease progression before the end of follow-up MISSING: otherwise

7. Proportion of patients who undergo complete resection during the procedure

Completeness of the resection will be defined as follows:

New variable	Rules
Complete resection	YES: if resection completeness = R0 (no residual tumour) NO: if resection completeness = R1 (microscopic residual tumour) OR R1 (other than microscopic residual tumour) OR R2 (macroscopic residual tumour) MISSING: otherwise

8. Proportion of patients who experience prolonged incision pain

Prolonged incision pain is defined as the need for analgesia after 5 weeks post-randomisation.

New variable	Rules
Prolonged incision pain	YES: if patient continuously prescribed analgesia until after 5 weeks post-randomisation that was not being taken preoperatively NO: if patient not continuously prescribed analgesia until after 5 weeks post-randomisation OR patient continuously prescribed analgesia that was administered pre-operatively until after 5 weeks MISSING: otherwise

9. General and disease-specific HRQoL: EORTC QLQ-C30, QLQ-LC13 and EQ5D to 1 year

The QLQ-C30, QLQ-LC13 and EQ5D questionnaires are completed at baseline, 2 weeks, 5 weeks, 3, 6 and 12 months. Details for how to derive the overall and sub-scale scores for these three questionnaires can be found below in the respective tables. The EORTC core questionnaire and associated modules scoring manual will be used to derive the QLQ-C30 and QLQ-LC13 scores ⁽¹⁾.

New variable – QLQ-C30	Rules
Global health status (QL2) raw score	At each time point: = mean of question 29 and 30, if both non-missing MISSING: otherwise
QL2 overall score	At each time point: = $[(\text{QL2 raw score}-1)/6] * 100$

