Upstaged to pN1	YES: if clinical disease stage of primary tumour = N0 AND pathological disease stage of primary tumour = N1 NO: if either: 
 pathological disease stage of primary tumour = N0 OR N2 clinical disease stage of primary tumour = N1 NOT CANCER: no cancer, sample benign MISSING: otherwise

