6.2.2 Analysis models

All outcomes listed in the study protocol will be presented as per the template tables **Table T11 to T18**. General methods of presentation and assessing treatment effects are outlined below. For all treatment comparisons, the open lobectomy group will be the reference group. Details specific to each outcome are described as appropriate.

Each outcome will be considered under a certain data type, as outlined in the table below:

Date type	Outcomes
Binary	Proportion of patients receiving adjuvant treatment Proportion of patients who undergo complete resection during the procedure Proportion of patients who experience prolonged incision pain Any in-hospital adverse event Any in-hospital serious adverse event
Categorical	Proportion upstaged to pN1 disease after the procedure Proportion upstaged to pN2 disease after the procedure
Time to event	Time from surgery to hospital discharge Time to uptake of adjuvant treatment Overall survival Disease-free survival
Longitudinal	Physical function (primary) Pain scores in the first two days post-surgery HRQoL (QLQ-C30, QLQ-LC13, EQ5D)

Each type of data will be summarised and compared between the groups according to the following:

- **Binary outcomes** will be presented as numbers and percentages of patients in each treatment group. Outcomes will be compared between treatment groups using generalised linear models, with treatment comparison estimates presented as adjusted risk ratios (RR) and risk differences (RD) with 95% confidence intervals (95% CI). Formal statistical comparisons of treatment effects will only be performed if more than ten patients in total experience the outcome (with at least one event in each treatment group).
- **Categorical outcomes** will be presented as numbers and percentages of patients in each treatment group in each category. Outcomes will be compared between treatment groups using multinomial logistic regression, with treatment comparison estimates presented as adjusted RR and 95% CI.

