6.2.8 Missing data

In all tables missing data for continuous variables will be indicated by footnotes. For category variables missing data will be highlighted by use of observation counts. If the amount of missing data differs substantially between treatment groups potential reasons will be explored.

Missing predictors:

There will be no missing data for any of the randomisation factors (by design). All other potential predictors are baseline measurements of continuous longitudinal outcomes, and due to the joint modelling approach described previously the handling of missing values for such data is considered in the context of missing longitudinal data (see below).

Missing outcomes measured at one time point:

- If the proportion of missing data is less than 5% then complete case analysis will be performed (i.e. excluding cases with missing data).
- If the proportion of missing data is above 5% multiple imputation methods will be considered. A general imputation model that uses an iterative procedure to generate imputed values will be used to generate multiple complete data sets (e.g. using Stata's `mi impute`). The model of interest will be fitted to each of the complete data sets and effect estimates combined using Rubin's rules. If appropriate, methods such as predictive mean matching will be used in order to ensure that imputed values lie within specific ranges.

Missing longitudinal data:

- For continuous data measured at multiple time points preoperative values will be modelled jointly with those measured postoperatively, as described previously, thereby allowing all cases with at least one observation to be included. If the proportion of cases that do not have at least one observation is above 5% then multiple imputation methods will be considered (see above). If appropriate (the level of missingness is >20%) then any variables that are predictive of missingness will be identified, and if there is reason to suggest that an assumption of missing at random (MAR) given these variables is reasonable (especially likely if the variable was measured pre-operatively) then such variables will be adjusted for in the models of interest. These models can be shown to provide unbiased estimates of the treatment effect and moreover multiple imputation approaches would not be expected to recover any additional information.

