FVC (% predicted)

DLCO (% predicted)

Medical history

Family history of lung cancer

Respiratory comorbidity

Neurological dysfunction

Diabetes mellitus

Alcoholism

Previous lung surgery

CVAT/TIAs

Cardiovascular comorbidity

Chronic pain syndrome

Deep vein thrombosis

Previously treated malignancy

Neoadjuvant treatment

Pre-operative treatment

Data are presented as median (interquartile range), mean (standard deviation), or n (%).

Table T5 Operative details

	Randomised to open (n=XX)		Randomised to VATS (n=XX)		Overall (n=XX)	
	n	%	n	%	n	%
Operative strategy						
Frozen section biopsy planned						
Biopsy attempted						
Biopsy diagnostic						
Malignancy confirmed						
Resection details						
Benign disease on frozen section						
Open and close (inoperable/extensive malignancy)						
Resection of airway without removal of lung parenchyma						
Pneumonectomy						
Lobectomy/bilobectomy						
Segmentectomy						
Wedge resection						
Lobectomy and segmentectomy						
Lobectomy and wedge resection						
Lobectomy and resection of airway without removal of lung parenchyma						
Benign disease on frozen section and lobectomy						
Benign disease on frozen section and wedge resection						
Operation details						
First operator classification	Consultant surgeon					
	Trainee surgeon					
Prophylactic mini-tracheostomy tube used						
Number of N1 lymph node stations sampled	0					
	1-2					
	3-4					
	5					
Number of N2 lymph node stations sampled	0					
	1-2					
	3-4					
	5-6					
Anterior thoracotomy performed						

Postero-lateral thoracotomy performed

Muscle sparing approach used

Serratus muscle 'spared'

Latissimus muscle 'spared'

Number of ports/incisions used

1
2
3
4

Duration of drain

Intra-operative analgesia

Single-shot paravertebral block

[figure not shown]
Epidural

Paravertebral catheter

Intercostal block

Other analgesia

Figure F3 Pathology flow chart

Notes: details of the resection in patients undergoing an alternative resection will be provided in footnotes

Table T6 Patient blinding at two days post-surgery

Intervention	VATS	Patient's answer, n (%)			Question not asked, n
		Open	Do not know	Total	
VATS					
Open					
Total					

Blinding index (VATS: open) = X.XX (95% confidence interval [CI], X.XX to X.XX): X.XX (95% CI, X.XX to X.XX) (P=X.XX).

Table T7 Patient blinding at discharge

Intervention	VATS	Patient's answer, n (%)			Question not asked, n
		Open	Do not know	Total	
VATS					
Open					
Total					

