Blinding index (VATS: open) = X.XX (95% confidence interval [CI], X.XX to X.XX): X.XX (95% CI, X.XX to X.XX) (P=X.XX).

Table T8 Nurse blinding at discharge

Intervention	VATS	Nurse's answer, n (%)			Question not asked, n
		Open	Do not know	Total	
VATS					
Open					
Total					

Blinding index (VATS: open) = X.XX (95% confidence interval [CI], X.XX to X.XX): X.XX (95% CI, X.XX to X.XX) (P=X.XX).

Table T9 Nurse blinding at 5 weeks

Intervention	VATS	Nurse's answer, n (%)			Question not asked, n
		Open	Do not know	Total	
VATS					
Open					
Total					

Blinding index (VATS: open) = X.XX (95% confidence interval [CI], X.XX to X.XX): X.XX (95% CI, X.XX to X.XX) (P=X.XX).

Table T10 Nurse blinding at 12 months

Intervention	VATS	Nurse's answer, n (%)			Question not asked, n
		Open	Do not know	Total	
VATS					
Open					
Total					

Blinding index (VATS: open) = X.XX (95% confidence interval [CI], X.XX to X.XX): X.XX (95% CI, X.XX to X.XX) (P=X.XX).

Table T11 Primary outcome

Outcome		Randomised to open (n=XX)		Randomised to VATS (n=XX)		Effect (95% CI)	p-value
		Mean/Median	SD/IQR	Mean/Median	SD/IQR		
Physical functioning	Baseline						
	2 weeks						
	5 weeks					MD/GMR	
	3 months						
	6 months						
	12 months						
Test for treatment*time interaction							
Overall treatment effect estimate						MD/GMR	

Notes: higher scores indicate higher levels of functioning
Analyses are adjusted for operating surgeon and centre

Figure F4 Primary outcome

[figure not shown]

Table T12 In-hospital secondary outcomes

Outcome	Randomised to open (n=XX)	Randomised to VATS (n=XX)	Effect (95% CI)	p-value
Duration of hospital stay (days)			HR	
Upstaged from cN0 to pN1 disease after procedure			HR	
Upstaged from cN0 to pN2 disease after procedure			RR/RD	
Complete R(0) resection during procedure			RR/RD	
Any in-hospital adverse event			RR/RD	
Any in-hospital serious adverse event			RR/RD	

Values are presented as median (interquartile range), mean (standard deviation), or n (%). Analyses are adjusted for operating surgeon and centre

Table T13 Post-discharge secondary outcomes

Outcome	Randomised to open (n=XX)	Randomised to VATS (n=XX)	Effect (95% CI)	p-value
Received adjuvant treatment			RR/RD	
Time to uptake of adjuvant treatment (months)			HR	
Overall survival (months)			HR	
Disease-free survival (months)			HR	
Prolonged incision pain			RR/RD	

Values are presented as median (interquartile range) or n (%).
Analyses are adjusted for operating surgeon and centre

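### pN2 upstaging and complete resection are not uniquely defined: the derivation rules, the analysis model and Table T12 disagree, and unresected or benign cases have no resection category

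*SAP*

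**What the plan says.** **pN2 upstaging.** Section 2.4 lists the outcome without a starting clinical stage. Section 5.2 item 5 derives it from pathology alone: "YES: if pathological disease stage of primary tumour = N2" and "NO: if pathological disease stage of primary tumour = N0 OR N1", with separate levels for benign samples (NOT CANCER) and MISSING. The parallel pN1 rule in item 10 does use clinical stage: "YES: if clinical disease stage of primary tumour = N0 AND pathological disease stage of primary tumour = N1". Table T12 labels the pN2 row "Upstaged from cN0 to pN2 disease after procedure".

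**Model and effect measure.** Section 6.2.2 classes both upstaging outcomes as categorical. For this class, "Outcomes will be compared between treatment groups using multinomial logistic regression", with adjusted RR as the estimate and no risk difference. Table T12 shows RR/RD for pN2 and HR for pN1.

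**Complete resection.** Item 7 codes "YES: if resection completeness = R0 (no residual tumour"), NO for R1 or R2, and MISSING for anything else. It has no level for benign disease or for a cancer that was not resected. Table T5 has a row "Open and close (inoperable/extensive malignancy"), and section 3.5 keeps patients found not to have lung cancer in the ITT analysis. For outcomes measured once, section 6.2.8 uses complete cases when under 5% are missing. Beyond that, "If the proportion of missing data is above 5% multiple imputation methods will be considered".

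**The concern.** These outcomes measure whether the operation is oncologically adequate; section 2.2 names pN2 upstaging as an oncological outcome. Two competent programmers working from this SAP could produce different pN2 counts, different denominators and different effect measures, and each could point to a passage in support.

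For complete resection there is also a possible direction of bias. An open-and-close operation for cancer is a known failure to achieve complete resection. If it is coded MISSING, it leaves the calculation or is replaced by a value modelled on patients who were resected. The R0 rate then rises, and it rises more in the arm with more such operations.

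**Working it through.** The SAP states no rate, power or sample size for these outcomes, so there is no figure to reproduce. The passages are compared first. The arithmetic only shows scale: 498 is the planned sample size in section 3, and every rate below is an assumption.

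**1. pN2 definition**

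| Patient | Item 5 (section 5.2) | Table T12 row |
|---|---|---|
| cN0, pN2 | YES | counted |
| cN1, pN2 | YES | outside the label |
| cN0 or cN1, pN0 or pN1 | NO | not counted |

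cN1 patients are foreseen: item 10 codes them explicitly and Table T4 has a clinical N1 row. The two counts therefore differ by exactly the number of cN1-to-pN2 patients. Nor does the T12 label say whether such a patient is a NO or leaves the denominator.

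Assume 5% benign (498 × 0.95 = 473.1 cancers), 6% pN2 among cN0, 3–10% of cancers cN1, and 10–30% pN2 among those.
- Difference: 473.1 × 0.03 × 0.10 = 1.4 to 473.1 × 0.10 × 0.30 = 14.2 patients.
- T12 count: 473.1 × 0.97 × 0.06 = 27.5 at 3% cN1; 473.1 × 0.90 × 0.06 = 25.5 at 10%.
- Item 5 count: 27.5 + 1.4 = 29.0 (after rounding) to 25.5 + 14.2 = 39.7, or 6.1% to 8.4% of cancers.
- The T12 count is 5.4–5.8% of all cancers but 6.0% of cN0 cancers, so the denominator matters too.

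**2. Effect measure**

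An exponentiated multinomial coefficient is a relative risk ratio, here the ratio between arms of P(YES)/P(NO). Assume pN2 is 10% v 15%.
- Risk ratio: 0.15/0.10 = 1.50.
- Relative risk ratio with 5% not cancer: (0.15/0.80)/(0.10/0.85) = 1.59.
- Relative risk ratio with 10% not cancer: (0.15/0.75)/(0.10/0.80) = 1.60.

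The HR against pN1 cannot be produced, because a pathology result has no event time.

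**3. Complete resection**

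Suppose no R status is recorded for open-and-close cancers. Assume 97% R0 among resected cancers, 1–3% of patients open-and-close and 3–8% benign.
- Coded MISSING and excluded: R0 rate 97.0%.
- Coded NO, at 1% open-and-close and 3% benign: 0.97 × 0.96/0.97 = 96.0%.
- Coded NO, at 3% open-and-close and 8% benign: 0.97 × 0.89/0.92 = 93.8%.
- Overstatement: about 1 to 3 percentage points.

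Between arms, assume 95% R0 among resected cancers in both, with 1% v 3% of cancers open-and-close. Coding them NO gives 0.95 × 0.99 = 94.1% v 0.95 × 0.97 = 92.2% (rounded), a difference of about 2 points. Excluding them gives 95% v 95%. With equal open-and-close rates, both arms would be inflated alike.

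The 5% threshold is 0.05 × 498 = 24.9, so 25 patients pass it. Benign cases at 8% would number about 40 (498 × 0.08) and would pass it alone; at 3% (about 15) they would not.

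**The case against.** A reader might infer that both rates have a wrong numerator or denominator. The documents do not support that.

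- Table T4 lists clinical N0 and N1 only. If no clinical N2 patient enters, every pN2 is an upstaging, and the pathology-only rule fits section 2.4. The pN1 rule needs its cN0 condition because a cN1 patient who is pN1 has not been upstaged, so the asymmetry between the two rules is not in itself an error.
- Section 1.4 calls the skeleton tables a guide, and the HR entry looks like a slip. But section 1.4 also expects reported content to be consistent with Appendix A, so the T12 conflict still needs resolving.
- Adjusted risk ratios can be obtained from a multinomial model's predicted probabilities. The SAP does not say whether this will be done, so RR is ambiguous but not shown to be misreported.
- The case report form is not shown. It may record R2 for open-and-close cancers, and item 7 would then code them NO. Their loss is conditional.
- Leaving benign cases out does not change the R0 rate among cancers and is defensible. The fault is in calling them missing.
- Above 5%, imputation is only considered. It is not automatic.

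All of this limits the claim. It does not remove the conflict between item 5 and Table T12, the conflict between section 6.2.2 and Table T12, or the absent categories in item 7.

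**Conclusion.** The point holds as one of inconsistent and incomplete definition. The pN2 conflict and the effect-measure conflict can be read directly from the text. The bias in complete resection depends on how R status is recorded for unresected cancers, which the SAP does not state, and a between-arm bias further requires that the arms differ in how often this happens.

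Under the assumptions shown, the pN2 count moves by about 1 to 14 patients on a base of about 26 to 28. The R0 rate is overstated by about 1 to 3 points, and a relative risk ratio read as a risk ratio would be 1.59–1.60 in place of 1.50. None of these rates comes from the SAP. The outcomes are secondary, but the correction is cheap and should be made.

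**What to change.** 1. Choose one pN2 definition and one denominator, and use them in both item 5 and Table T12. One option is cN0–1 to pN2 among patients with cancer, with cN0 to pN2 shown separately.
2. Report RR and RD for both upstaging outcomes, either from the binary generalised linear model among patients with cancer or from multinomial predicted probabilities. State which in section 6.2.2, and replace the HR entry for pN1 in Table T12.
3. In item 7, code cancers explored but not resected as NO and add a NOT CANCER level, as in items 5 and 10. State in section 6.2.8 that this level does not count towards the missing-data proportion and is not imputed.

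The cost is SAP wording, documented as an amendment under section 1.2, and derivation code. Clinical stage, pathological stage, resection type and benign status already appear in the SAP's derivations or tables, so no new data are needed.

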3.5 Analysis population

The analysis population consists of all randomised patients excluding:

- Patients who died after randomisation but prior to any data collection.

- Patients withdrawn who were unwilling for data collected to be used.

The main study analyses will be performed on an ITT basis, including randomised participants who are not found to have lung cancer. A modified ITT analysis excluding these participants will also be performed for the primary outcome.

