- **Time to event outcomes** will be summarised by the median and IQR or mean and SD in each treatment group, estimated from survival modelling. Outcomes will be compared using Cox’s proportional hazards, parametric models, or interval censoring methods for analysing discrete time data, as appropriate. The choice of model used will depend on the outcome event and the distribution of the data. Treatment comparisons will be presented as hazard ratios (HRs) and 95% CI if a proportional hazards model is used, time ratios (TRs) and 95% CI if an accelerated failure time model is used, or OR and 95% CI if a discrete time proportional odds model is used. Times will be censored using censoring variables defined below:

Outcome	Censor variable
Time from surgery to hospital discharge	Date of death, if patient died before hospital discharge
Time to uptake of adjuvant treatment	Last visit date, if patient did not receive any adjuvant treatment
Overall survival	Last visit date, if patient was alive at the end of the study follow-up
Disease free survival	Last visit date, if patient was disease free at the end of the study follow-up

- **Continuous longitudinal outcomes** will be summarised as means and SDs (or medians and IQRs if distributions are skewed) at each time point. Outcomes will be compared using linear mixed effects methodology with the treatment group and study design variables fitted as per section 5.2.1, and patient terms fitted as random effects. Separate parameter estimates will be incorporated into models for 1) the mean baseline response across both treatment groups and 2) at each post-intervention time point for each treatment (i.e. saturated model with time fitted as a categorical variable). If the time x treatment interaction (post-intervention) is not statistically significant at the 10% level an overall treatment effect will be reported. If the interaction is statistically significant the changes in treatment effect with time will be described. Deaths will be accounted for by modelling HRQoL and survival jointly. When modelling EQ5D, patients who have died will be assigned a score of 0 for all future time points. Different variance/covariance structures will be explored, and the structure that provides the best fit in terms of information criteria such as AIC, BIC and likelihood ratio tests will be used. Treatment comparisons will be presented as adjusted differences in means with 95% CI.

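### Disease-free survival is derived as time to recurrence alone, so a patient who dies without recurrence is censored and not counted as an event

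*SAP*

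**What the plan says.** Section 5.2, item 6 of the SAP announces the comparison: "Both overall and disease-free survival to 12 months will be compared between groups". Four variables follow.

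- Two serve OS: time from randomisation to death, and a flag whose event category is "NO: if patient died before the end of follow-up".
- The other two concern progression. The time is "Date of earliest disease recurrence – randomisation date". The flag is censored under "YES: if patient did not have disease progression before the end of follow-up" and is an event under "NO: if patient had disease progression before the end of follow-up".

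No variable in the list is called disease-free survival, and no variable combines recurrence with death.

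The censoring table in section 6.2.2 has a DFS row: "Last visit date, if patient was disease free at the end of the study follow-up". It has no entry for a patient who died without recurrence. Table T13 reports a hazard ratio on a line labelled disease-free survival, and section 6.2.6 plans a sensitivity analysis of the same outcome adjusted for pathological stage.

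Section 3.5 removes from the analysis population "Patients who died after randomisation but prior to any data collection". Section 6.2 uses that population for all primary and secondary outcomes.

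**The concern.** Disease-free survival is a composite: a patient stops contributing disease-free time on recurrence or on death, whichever comes first. The derived variables recognise only the first of these. A death without recurrence, for example a peri-operative one, is treated in the same way as the end of follow-up in a healthy survivor.

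The result is a hazard ratio for one quantity under the name of another. A reader of Table T13 would take the DFS line to include non-recurrence deaths. If such deaths differed between VATS and open surgery, the DFS line would not register the difference, in either direction.

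**Working it through.** **1. Apply the rules to each type of patient.** The SAP states no rate, event count or power for DFS, so there is no figure to reproduce. The check is to run the section 5.2 and 6.2.2 rules as written.

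| Course to 12 months | DFS as derived | DFS as named | OS as derived |
|---|---|---|---|
| Recurrence, alive | Event at recurrence | Event at recurrence | Censored |
| Recurrence, then death | Event at recurrence | Event at recurrence | Event |
| Death without recurrence | **Censored** | **Event at death** | Event |
| Alive, no recurrence | Censored | Censored | Censored |

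Only the third row is wrong. The flag's residual missing category does not catch it, because a patient who died without recurrence satisfies the censored condition. Section 6.2.2 does not repair it either: its DFS row covers those disease free at the end of follow-up, so the date at which this patient leaves the risk set is also not fixed. By contrast, the row for hospital discharge in the same table does name the date of death.

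**2. Share of events lost.** Let r be the 12-month proportion with recurrence and d the proportion dying without recurrence. The share of true DFS events that becomes censored is d / (r + d). Both rates are assumptions. N = 498 is the planned sample size (SAP section 3).

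| r | d | Share lost | Events lost, 498·d | True DFS events, 498·(r + d) |
|---|---|---|---|---|
| 12% | 2% | 0.02/0.14 = 14% | 10 | 70 |
| 6% | 2% | 0.02/0.08 = 25% | 10 | 40 |
| 12% | 5% | 0.05/0.17 = 29% | 25 | 85 |
| 6% | 5% | 0.05/0.11 = 45% | 25 | 55 |
| 10% | 3% | 0.03/0.13 = 23% | 15 | 65 |

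**3. Cross-check with competing hazards.** Let the cause-specific hazards be constant over one year, with λr = −ln(1 − r) and λd = −ln(1 − d). Expected recurrences are N·[1 − e^−(λr+λd)]·λr/(λr + λd), and deaths without recurrence follow likewise. At 10% and 3% this gives 49.1 events as coded and 63.2 composite events, so 14.2 are lost (22%). This agrees with the simple ratio. Over a wider assumed grid (r 5–15%, d 1–5%) the share lost runs from 6% to 50%.

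**4. What the hazard ratio can miss.** Assume recurrence of 10% in both arms, and death without recurrence of 5% in the open arm and 2% in the VATS arm.

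- As coded (recurrence only): HR = 0.1054 / 0.1054 = 1.00.
- Composite, VATS against open: (0.1054 + 0.0202) / (0.1054 + 0.0513) = 0.1256 / 0.1567 = 0.80.
- With the two death rates exchanged: 0.1567 / 0.1256 = 1.25.

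The coded HR stays at 1.00 in both cases.

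**The case against.** The strongest reply is that the text is incomplete more than wrong. Item 6 lists death and progression variables together under one title, no line says that the progression pair alone is DFS, and a programmer could combine them. The protocol, not shown here, may define DFS, and section 2.2 groups it with oncological outcomes, which could mean that recurrence was the target. This does not remove the point. The SAP is the document that fixes the derivation, the only non-OS event it defines is progression, and if recurrence was intended then the label is wrong. Either the name or the derivation has to change.

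The reply does stand on several points of scope, where a reader might infer too much:

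- **That OS also misses deaths.** It does not: section 5.2 makes death the OS event.
- **That section 3.5 deletes early deaths from the survival analyses.** The data-collection table in section 4 schedules patient characteristics and questionnaires before randomisation. Read literally, the exclusion therefore applies to nobody. It could remove deaths only if it were taken to mean data collected after randomisation, which the SAP does not say.
- **That all deaths are lost from DFS.** Only those without prior recurrence are.
- **That the HR is biased because censoring gives the dead the survivors' later risk of recurrence.** A cause-specific hazard ratio does not need that assumption. It would matter for event probabilities or medians by arm. For the HR, the fault is that it estimates something other than DFS.
- **That these deaths disappear from the report.** They count in OS, and the safety population in section 3.6 has no exclusion for early deaths.

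**Conclusion.** Wrong as written for the named endpoint. Under the SAP's rules, the DFS hazard ratio in Table T13 and the stage-adjusted DFS analysis in section 6.2.6 compare the cause-specific hazard of recurrence. This conclusion rests on the text alone.

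The size rests wholly on assumed rates. About 14–45% of true DFS events would be censored with recurrence of 6–12% and death without recurrence of 2–5%, and the top of that range pairs the lowest recurrence with the highest mortality. The central illustration is 15 of 65 events. The hazard ratios of 0.80 and 1.25 show that a difference between arms could be missed; they do not predict one.

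DFS is one of eleven secondary outcomes, and the SAP's only power statement concerns physical function, so the primary result is unaffected. The section 3.5 wording is a minor clarification.

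**What to change.** In section 5.2, item 6, add a variable named for DFS:

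- **Time:** the earlier of first recurrence and death from any cause, minus the randomisation date.
- **Event:** either of these.
- **Censoring:** only patients alive and recurrence-free, at the date of their last assessment.

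Change the DFS row of the section 6.2.2 censoring table to match. Table T13 and the section 6.2.6 analysis then follow without further change.

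If recurrence alone is also wanted, report it separately under that name, with cumulative incidence treating death as a competing event.

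In section 3.5, state that the exclusion for death before data collection does not apply to OS and DFS, so that it cannot be read as taking early deaths out of an intention-to-treat analysis.

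The cost is a SAP amendment and one derived variable. Death dates are already used for OS, so no new data are needed. The change should be made before any comparative analysis of DFS.
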